#### **7.6.1.1 Gastrointestinal Dose-limiting Toxicity**

Any of the following study treatment-related events will be considered a GI DLT:

- Grade 2 colitis that lasts longer than 5 days.

- Grade  $\geq$  3 diarrhea or colitis, regardless of duration.

#### **7.6.1.2 Hepatic Dose-limiting Toxicity**

Any of the following study treatment-related events will be considered a hepatic DLT:

- Grade 4 elevations in serum transaminases (AST and ALT), alkaline phosphatase (ALP), or total bilirubin.
- Grade 3 elevations in serum AST, ALT, or ALP that last longer than 5 days or are associated with clinical symptoms or bilirubin  $> 2 \times$  ULN in the absence of cholestasis.
- Grade 2 elevations in AST or ALT with symptomatic liver inflammation (eg, right upper quadrant tenderness, jaundice).
- AST or ALT  $> 3 \times$  ULN and concurrent total bilirubin  $> 2 \times$  ULN without initial findings of cholestasis (elevated ALP; eg, findings consistent with Hy's law or FDA definition of potential drug-induced liver injury [p-DILI]). Note that this specific category of DLT uses ULN rather than CTCAE grade for definition.

Any of the following study treatment-related events will be considered a hepatic DLT for participants with HCC:

- ALT or AST  $> 20 \times$  ULN, regardless of duration.
- ALT or AST  $> 10 \times$  ULN for greater than 2 weeks.
- Total bilirubin  $> 8 \times$  ULN regardless of duration for participants with elevated bilirubin at study entry or  $> 5 \times$  ULN for participants with normal bilirubin at study entry.
- ALT or AST  $> 3 \times$  ULN and concurrent total bilirubin  $> 2 \times$  ULN.

#### **7.6.1.3 Hematologic Dose-limiting Toxicity**

Any of the following study treatment-related events will be considered a hematologic DLT:

- Grade 4 neutropenia  $\geq 7$  days in duration.
- Grade 4 thrombocytopenia.
- Grade 3 thrombocytopenia with bleeding or any requirement for platelet transfusion.
- Febrile neutropenia that lasts longer than 48 hours.
- Grade 3 hemolysis (ie, requiring transfusion or medical intervention such as steroids).

#### **7.6.1.4 Dermatologic Dose-limiting Toxicity**

Any of the following study treatment-related events will be considered a dermatologic DLT:

- Grade 4 rash.
- Grade 3 rash if no improvement (ie, resolution to  $\leq$  Grade 1) after a 1- to 2-week infusion delay.

### **7.6.1.5 Other Dose-limiting Toxicities**

Any of the following events will be considered a DLT:

- Grade 2 drug-related uveitis, episcleritis, iritis eye pain, or blurred vision that does not respond to topical therapy and does not improve to Grade 1 severity within the re-treatment period OR requires systemic treatment.
- Grade 3 drug-related uveitis, episcleritis, iritis, pneumonitis, bronchospasm, or neurologic toxicity.
- Grade  $\geq 4$  hypersensitivity reaction or Grade 3 that does not resolve to Grade 1 in  $< 6$  hours.
- Other  $\geq$  Grade 3 study treatment-related toxicity will be considered a DLT. However, the following Grade 3 or 4 events will **not** be considered DLTs:
  - Grade 3 or Grade 4 electrolyte abnormalities that are not complicated by associated clinical adverse experiences, last less than 48 hours, and either resolve spontaneously or respond to conventional medical intervention. Confirmatory laboratory test is required within 48 hours.
  - Grade 3 nausea or vomiting that lasts less than 48 hours, and either resolves spontaneously or responds to conventional medical intervention.
  - Grade 3 or Grade 4 elevation of amylase or lipase not associated with clinical or radiographic evidence of pancreatitis.
  - Grade 3 fever not associated with hemodynamic compromise (eg, hypotension, clinical or laboratory evidence of impaired end-organ perfusion).
  - Grade 3 endocrinopathy that is well controlled by hormone replacement.
  - Grade 3 tumor flare (defined as pain, irritation, or rash that localizes to sites of known or suspected tumor).
  - Grade 3 fatigue.
  - Grade 3 infusion reaction that returns to Grade 1 in  $< 6$  hours.

### **7.6.2 Management Algorithms for Immuno-oncology Agents**

I-O agents are associated with imAEs that can differ in severity and duration from AEs caused by other therapeutic classes. BMS-986218, ipilimumab, and nivolumab are considered I-O agents in this protocol. Early recognition and management of imAEs associated with I-O agents may mitigate severe toxicity. Management algorithms have been developed from extensive experience with ipilimumab and nivolumab to assist Investigators in assessing and managing the following groups of imAEs:

- GI
- Renal
- Pulmonary
- Hepatic
- Endocrinopathies
- Skin

- Neurological
- Myocarditis

The clinical nature of AEs noted with BMS-986218 will determine the role of the algorithms for use in toxicities related to its use in this study. The algorithms recommended for the management of imAEs in this protocol are in [Appendix 10](#).

### **7.6.3 Dose Delays Due To Toxicity**

Participants who experience the following due to any cause must have all study treatment(s) withheld:

- Potential DLTs, until DLT relatedness is defined.
- Select AEs and laboratory abnormalities:
  - $\geq$  Grade 2 pneumonitis.
  - $\geq$  Grade 2 abnormality in AST, ALT, or total bilirubin.
  - $\geq$  Grade 2 creatinine.
  - $\geq$  Grade 2 diarrhea or colitis.
  - $\geq$  Grade 2 neurological AE.
  - AE, laboratory abnormality, or concurrent illness that, in the judgment of the Investigator, warrants delaying study treatment administration.
  - Confirmed SARS-CoV-2 infection.

Criteria for participants who are required to permanently discontinue study treatments is listed in [Section 8.2](#). Participants not meeting guidelines for permanent discontinuation will be permitted to resume therapy based on the criteria specified below in Section 7.6.3.1. Participants eligible to resume study therapy will resume study therapy at the nominal treatment visit following their last received study medication dose.

The end of cycle tumor assessments, such as CT, magnetic resonance imaging (MRI), or positron emission tomography (PET), will continue on a Q8W schedule relative to the participant's first dose, regardless of any treatment delay incurred.

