**Efficacy Assessments:**

- Efficacy assessments for the anti-tumor activity of BMS-986218, alone and in combination with nivolumab, will be based on tumor measurements, using RECIST v1.1 or per PCWG 3 criteria for prostate, with computed tomography and/or magnetic resonance imaging, as appropriate, at baseline and Q8W ( $\pm$  1 week) for the Q4W and Q2W dosing regimens during the treatment period, except the Randomized BMS-986218 Monotherapy Cohort Expansion in Cutaneous Melanoma (Part 2A), where tumor assessment in participants receiving BMS-986218 or ipilimumab will occur at 12 weeks from first dose ( $\pm$  1 week), prior to initiating the next cycle of treatment. After that, subsequent tumor imaging assessments to be performed Q8W ( $\pm$  1 week). Tumor imaging assessments are to be performed prior to initiating next cycle of treatment.
- Efficacy assessments for the anti-tumor activity of ipilimumab are to be performed 12 weeks from first dose, regardless of dose delays, if any ( $\pm$  1 week). Tumor imaging assessments are to be performed prior to initiating next cycle of treatment. Participants who remain free of subsequent therapy will undergo the second tumor imaging assessment at 24 weeks from first dose  $\pm$  1 week. After that, participants who remain free of subsequent therapy will undergo tumor imaging assessment Q8W ( $\pm$  1 week) until subsequent tumor-directed therapy is initiated or until 48 weeks after discontinuation of study treatment/EOT visit, and then Q12W ( $\pm$  2 weeks) for a total duration of 2 years.
- Images will be submitted to an imaging core lab. Image acquisition guidelines and submission process will be outlined in the CA022001 Imaging Manual to be provided by the core laboratory.

**Data Monitoring Committee:** No.

BMS has developed a multi-layered process to ensure safety monitoring through close collaboration of study site Investigators, the BMS study team, and the BMS Worldwide Patient Safety (WWPS)-led Safety Management Team

(SMT). This collaborative process constitutes the safety monitoring plan for the study. To support safety oversight, BMS has established ongoing processes for collection, review, analysis, and submission of individual AE reports and their aggregate analyses. Because this is an open-label study, WWPS, the BMS Medical Monitor, and the Investigators will have access to all data necessary for safety evaluation.

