**Table 2-2:**

**On-Treatment - Schedule of Activities for Q4W Dosing Schedules in BMS-986218 Monotherapy Escalation (Part 1A), Safety Evaluation of Combination Doses of BMS-986218 with Nivolumab (Part 1B), Randomized BMS-986218 Monotherapy Cohort Expansion in Cutaneous Melanoma (Part 2A), Randomized BMS-986218 Monotherapy Cohort Expansion (Part 2B), and Combination Cohort Expansions (Part 2C and Part 2D)**

Procedure	Cycle 1 (28 Days in Length) (Visit Window $\pm$ 2 Days, except for C1D1)	Cycle 2 (28 Days in Length) (Visit Window $\pm$ 2 Days)		Cycles 3 and Beyond (Each Cycle 28 Days in Length) (Visit Window $\pm$ 2 Days)	EOT a,b	Notes					
	DLT Period is Cycles 1 and 2										
	D1	D8	D15	D22	D1	D8	D15	D22	D1	EOT a,b	Notes
Imaging Assessments											
Body Imaging	
Tumor imaging assessment to be performed Q8W from first dose (<math>\pm</math> 1 week), prior to initiating next cycle of treatment (for Part 1A, Part 1B, Part 2B, Part 2C, and Part 2D).
 
Tumor imaging assessment to be performed at 12 weeks from the first dose, regardless of dose delays, if any (<math>\pm</math> 1 week), prior to initiating the next cycle of treatment, for participants in the Randomized BMS-986218 Monotherapy Cohort Expansion in Cutaneous Melanoma (Part 2A). After that, subsequent tumor imaging assessments to be performed Q8W (<math>\pm</math> 1 week), prior to initiating the next cycle of treatment.
 
Participants who remain free of subsequent therapy will undergo tumor imaging assessment Q8W (<math>\pm</math> 1 week) until subsequent tumor-directed therapy is initiated or until 48 weeks after discontinuation of study treatment/EOT visit, and then Q12W (<math>\pm</math> 2 weeks) for a total duration of 2 years.
							
The same imaging modality is to be used for all assessments, per RECIST v1.1 (Appendix 5) or per PCWG 3 criteria for prostate (Appendix 12). Tumor assessment to be performed prior to initiating next cycle of treatment. CT and MRI scans should be acquired with slice thickness of 5 mm or less with no intervening gap (contiguous). Every attempt should be made to image each participant using an identical acquisition protocol on the same scanner for all imaging timepoints.
			

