**Table 2-4: On-Treatment - Schedule of Activities for Q3W Dosing Schedule for Ipilimumab in the Randomized BMS-986218 Monotherapy Cohort Expansion in Cutaneous Melanoma (Part 2A)**

Procedure	Cycle 1 (21 Days in Length) (Visit Window $\pm$ 2 Days, except for C1D1)			Cycle 2 (21 Days in Length) (Visit Window $\pm$ 2 Days)			Cycle 3 and Cycle 4 (21 Days in Length) (Visit Window $\pm$ 2 Days)			EOT a,b	Notes
	D1	D8	D15	D1	D8	D15	D1	D8	D15		
Adverse Event Reporting and Concomitant Medication Assessments											
Monitor for Non-SAEs	Non-SAEs will be collected starting with the first dose of study medication and through 100 days following last dose of study treatment.									Section 9.2 and Appendix 3.	All AEs (SAEs or nonserious AEs) including those associated with SARS-CoV-2 infection must be collected continuously during the treatment period
Monitor for SAEs	All SAEs must be collected from the date of the participant's written consent until 100 days following the last dose of study treatment.									Section 9.2 and Appendix 3.	
Concomitant Medications	X	X	X	X	X	X	X	X			
PK Assessments											
Serial Blood Sampling	See Table 9.5-4 of the PK and immunogenicity sampling schedule and Section 9.5.										
Immunogenicity (ADA) Assessments	See Table 9.5-4 of the PK and immunogenicity sampling schedule and Section 9.5.										
Imaging Assessments											
Body Imaging	Tumor imaging assessment to be performed at 12 weeks from the first dose, regardless of dose delays, if any ( $\pm$ 1 week). After that, subsequent tumor imaging assessments to be performed Q8W ( $\pm$ 1 week). Participants who remain free of subsequent therapy will undergo tumor imaging assessment Q8W ( $\pm$ 1 week) until subsequent tumor-directed therapy is initiated or until 48 weeks after discontinuation of study treatment/EOT visit, and then Q12W ( $\pm$ 2 weeks) for a total duration of 2 years.									The same imaging modality is to be used for all assessments, per RECIST v1.1 (Appendix 5). CT and MRI scans should be acquired with slice thickness of 5 mm or less with no intervening gap (contiguous). Every attempt should be made to image each participant using an identical acquisition protocol on the same scanner for all imaging timepoints.	

**Table 2-4: On-Treatment - Schedule of Activities for Q3W Dosing Schedule for Ipilimumab in the Randomized BMS-986218 Monotherapy Cohort Expansion in Cutaneous Melanoma (Part 2A)**

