#### **7.6.4      *Exceptions to Permanent Discontinuation Criteria***

Any drug-related AE occurring at any time that meets DLT criteria as outlined in Section 7.6.1 will require permanent discontinuation, **with the exception of the following:**

- Grade 3, nausea, vomiting, or abdominal pain that returns to Grade 1 or baseline within or at 48 hours either spontaneously or with medical intervention.
- Grade 3 pruritus or rash that returns to Grade 1 or baseline within 7 days with medical intervention.
- Isolated Grade 3 or 4 electrolyte imbalances/abnormalities that are not associated with clinical sequelae and are corrected with supplementation/appropriate management within 3 days of their onset.
- Grade 4 neutropenia < 7 days in duration.
- Grade 4 lymphopenia or leukopenia.
- Grade 3 increase in amylase or lipase that is not associated with clinical or radiographic evidence of pancreatitis.
- Grade 3 infusion reactions that return to Grade 1 in < 6 hours.

- Grade 3 fever not associated with hemodynamic compromise (eg, hypotension, clinical, or laboratory evidence of impaired end-organ perfusion).
- Grade 3 tumor flare (defined as pain, irritation, or rash that localizes to sites of known or suspected tumor).
- Grade 3 fatigue.
- Grade 3 or 4 drug-related endocrinopathy AEs, such as adrenal insufficiency, adrenocorticotropic hormone, hyper- or hypothyroidism, or glucose intolerance, which resolve or are adequately controlled with physiologic hormone replacement (corticosteroids, thyroid hormones) or glucose-controlling agents, respectively, may not require discontinuation after discussion with and approval from the BMS Medical Monitor (or designee).
- Any event that leads to delay in dosing, lasting > 8 weeks from the previous dose, requires discontinuation, with the exception of the following:
  - Dosing delays for prolonged steroid tapers to manage drug-related AEs are allowed. Prior to re-initiating treatment in a participant with a dosing delay lasting > 8 weeks from the previous dose, the BMS Medical Monitor (or designee) must be consulted. Tumor assessments should continue as per protocol even if dosing is delayed. Periodic study visits to assess safety and laboratory studies should also continue Q4W, or more frequently if clinically indicated, during such dosing delays.

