### **9.3          Efficacy Assessments**

Efficacy assessments for the anti-tumor activity of BMS-986218, alone and in combination with nivolumab, will be based on tumor measurements using RECIST v1.1 or per PCWG 3 criteria for prostate with CT and/or MRI, as appropriate, at baseline, and during the treatment period. Tumor imaging assessments are to be performed prior to initiating next cycle of treatment.

Tumor assessments will occur every 8 weeks (Q8W) for participants receiving BMS-986218 and nivolumab for all study parts, except the Randomized BMS-986218 Monotherapy Cohort Expansion in Cutaneous Melanoma (Part 2A), where tumor assessment in participants receiving BMS-986218 or ipilimumab will occur at 12 weeks from first dose ( $\pm$  1 week), prior to initiating the next cycle of treatment. After that, subsequent tumor imaging assessments are to be performed Q8W ( $\pm$  1 week), prior to initiating the next cycle of treatment. Participants who remain free of subsequent therapy will undergo tumor imaging assessment Q8W ( $\pm$  1 week) until subsequent

tumor-directed therapy is initiated or until 48 weeks after discontinuation of study treatment/EOT visit, and then Q12W ( $\pm$  2 weeks) for a total duration of 2 years.

Only data for the procedures and assessments specified in this protocol should be submitted to the Sponsor or Designee on a CRF. Additional procedures and assessments may be performed as part of standard of care. However, data for these assessments should remain in the participant's medical record and should not be provided to the Sponsor or Designee, unless specifically requested from BMS or designee.

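### Section 7.6.3 sets scans after a treatment delay at Q8W from first dose with no Part 2A exception, so read literally it moves delayed Part 2A participants off the Part 2A scan calendar

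*Combined protocol and SAP*

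**What the plan says.** Section 7.6.3 applies to any participant with a listed event, who "must have all study treatment(s) withheld"; nothing limits it by study part or arm. It then says that end-of-cycle tumor assessments "will continue on a Q8W schedule relative to the participant's first dose, regardless of any treatment delay incurred".

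For Part 2A, Tables 2-2 (BMS-986218 arms) and 2-4 (ipilimumab arm) both say: "Tumor imaging assessment to be performed at 12 weeks from the first dose, regardless of dose delays, if any". Both continue: "After that, subsequent tumor imaging assessments to be performed Q8W". Section 9.3 sets 8-weekly assessments "for all study parts, except the Randomized BMS-986218 Monotherapy Cohort Expansion in Cutaneous Melanoma (Part 2A"), where the first assessment "will occur at 12 weeks from first dose". Section 5.1.2 makes the same exception. Section 7.6.3 does not.

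Two other places bear on the question. Section 7.6.4, on prolonged dosing delays, says: "Tumor assessments should continue as per protocol even if dosing is delayed". The synopsis, in a separate bullet on ipilimumab, says that participants free of subsequent therapy "will undergo the second tumor imaging assessment at 24 weeks from first dose", followed by Q8W. That differs from Table 2-4 and from the synopsis's own preceding bullet.

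**The concern.** Section 7.6.3 and the Part 2A tables both address the participant with a delay, and they give different dates. Section 7.6.3 is where a site would look when treatment is withheld, and its triggers are broad: several Grade 2 or higher events, confirmed SARS-CoV-2 infection, or investigator judgement.

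PFSR at 24, 36 and 48 weeks is a primary endpoint (Table 4-1). For Part 2A, Table 10.3.1-1 estimates the PFSR difference from ipilimumab. Progression is dated when it is documented, so the scan calendar decides whether a progression shortly before a landmark is counted by that landmark. If the calendar changes because a participant had a toxicity delay, PFSR depends partly on toxicity. Delay rates can differ between arms: ipilimumab stops after at most 4 doses, while BMS-986218 runs Q4W for up to 2 years at three dose levels.

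**Working it through.** The plan gives no figure to reproduce. The check derives the calendars, compares them at the PFSR landmarks, and then illustrates the size.

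**1. Calendars.** The documents do not list these weeks; they follow from the rules.

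| | Source | Weeks from first dose |
|---|---|---|
| A | Section 7.6.3, read literally | 8, 16, 24, 32, 40, 48 |
| B | Tables 2-2 and 2-4, Sections 5.1.2 and 9.3 | 12, 20, 28, 36, 44, 52 |
| C | Synopsis, ipilimumab bullet | 12, 24, 32, 40, 48 |

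Each scan on A is 4 weeks from the nearest scan on B. With the 1-week window either side used in the tables, week 8 covers weeks 7 to 9 and week 12 covers weeks 11 to 13. The windows never overlap, so one set of scans cannot satisfy both.

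**2. Last scan at or before each landmark.**

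| Landmark | A | B | C |
|---|---|---|---|
| 24 weeks | 24 | 20 | 24 |
| 36 weeks | 32 | 36 | 32 |
| 48 weeks | 48 | 44 | 48 |

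**3. Illustration for participants who switch from B to A.** Assume exponential PFS with median m, S(t) = 0.5^(t/m), and progression found only at on-time scans, so that observed PFSR(t) = S(last scan at or before t). The documents give no median PFS; m is assumed. Differences are from unrounded values.

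| m (weeks) | Week 24 on A = S(24) | Week 24 on B = S(20) | B minus A, week 24 | B minus A, week 36 | B minus A, week 48 |
|---|---|---|---|---|---|
| 8 | 12.5% | 17.7% | +5.2 | -1.8 | +0.6 |
| 12 | 25.0% | 31.5% | +6.5 | -3.2 | +1.6 |
| 16 | 35.4% | 42.0% | +6.7 | -4.0 | +2.4 |

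The sign reverses at week 36 because there B has the later scan. For example, at m = 12, S(36) = 12.5% on B and S(32) = 15.7% on A.

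The choice of m does not hide a larger week-24 gap. With u = 0.5^(4/m), the gap is u^5 - u^6, which is largest at u = 5/6: (5/6)^5 x (1/6) = 0.402 x 0.167 = 0.067, or 6.7 points.

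**4. Effect on an arm difference.** The shift is the difference in the share switching calendar times the gap. With m = 12 and assumed shares:

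- 40% against 20%: 0.20 x 6.5 = 1.3 points
- 60% against 20%: 0.40 x 6.5 = 2.6 points

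**5. Precision for scale.** With 33 per arm (Section 10.1.3), PFSR near 30% and a simple binomial approximation, the 95% half-width for an arm difference is 1.96 x sqrt(2 x 0.30 x 0.70 / 33) = 1.96 x 0.113 = 0.22, or about 22 points.

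**The case against.** The best defence is that the Part 2A rule is the more specific one and already covers delays. Sections 5.1.2 and 9.3 expressly take Part 2A out of the general 8-weekly rule. Section 7.6.4 keeps assessments on the protocol schedule, and Section 9 requires adherence to the Schedule of Activities. The verb in Section 7.6.3 presupposes a schedule already in use, and the sentence is evidently meant to anchor scans to first dose. Both calendars count from first dose, so a delay in itself moves neither. All of this stands as an argument about what sites will probably do. It does not remove the conflict: Section 7.6.4 names no calendar, and Section 7.6.3 names one that is not Part 2A's.

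The conflict is also narrower than it may look. In the tables, the words about dose delays attach only to the week-12 scan; weeks 20 and 28 follow from the next sentence, and Sections 5.1.2 and 9.3 do not mention delays. Applying Section 7.6.3 to the ipilimumab arm is less natural, because it speaks of end-of-cycle scans and week 8 is not the end of a 3-week cycle. If the synopsis bullet governed that arm, its last scan before each landmark would be the same as under Section 7.6.3 (calendars A and C above), and a switch would change nothing at those landmarks.

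The illustration overstates the likely effect. Deaths count as PFS events when they occur, and Section 9.3.1 allows unscheduled scans; both narrow the gap. A delay after week 24 cannot affect week-24 PFSR. Drug-related events meeting DLT criteria generally lead to discontinuation rather than delay (Sections 7.6.1 and 8.1, with exceptions in 7.6.4). Section 3.2.1 says that no prospective hypothesis is formally evaluated.

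**Conclusion.** This is an internal inconsistency with a modest likely effect. Section 7.6.3, followed as written, gives a delayed Part 2A participant a different scan calendar from the tables, and no window reconciles the two. The sizes in the working are upper bounds for participants who actually switch. They rest on exponential PFS, on-time scans as the only means of detection, assumed medians and assumed delay shares. The resulting shift of about 1 to 3 points is small against the precision of a Part 2A comparison. It is still worth removing, because it would be systematic and tied to toxicity.

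A reader might infer two stronger things. One is that delayed Part 2A participants will be moved to weeks 8, 16 and 24. The documents do not support that: other sections point towards the Part 2A calendar, and the text permits the switch without clearly requiring it. The other is that ORR is distorted too. ORR rests on best overall response across all timepoints, and no effect of a four-week offset on it has been shown.

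**What to change.** Reword the Section 7.6.3 sentence to say that tumor assessments stay on the study part's own Schedule of Activities calendar, counted from first dose, regardless of treatment delay: for Part 2A, week 12 and then Q8W as in Tables 2-2 and 2-4; for the other parts, Q8W.

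In the same edit, reconcile the synopsis bullet on ipilimumab with Table 2-4 and with the synopsis's preceding bullet, so that all four Part 2A arms share one scan calendar. Changing Section 7.6.3 alone would leave that second conflict open, and that one can separate the control arm from the BMS-986218 arms even without a delay.

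The cost is one sentence in Section 7.6.3 and one correction in the synopsis. No scans are added to those already in the Schedule of Activities.
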